$\widehat{CDF}_{pbo,j}(t = D180)$ and $SE(\widehat{CDF}_{pbo,j}(t = D180))^2$ are the cumulative distribution function estimate at Day 180 in the placebo group in the jth stratum and its variance, respectively.

$\widehat{CDF}_{trt,j}(t = D180)$ and $SE(\widehat{CDF}_{trt,j}(t = D180))^2$ are defined similarly in the itacitinib group for jth stratum subjects. $TS_{Day180NRM}$ will be asymptotically distributed as a Chi-square test statistic with degree of freedom equal to 1.

The overall estimate of treatment difference in Day 180 NRM between placebo and itacitinib is thus defined as the following:

$$w * [\widehat{CDF}_{pbo,standard}(t = D180) - \widehat{CDF}_{trt,standard}(t = D180)] + (1 - w) * [\widehat{CDF}_{pbo,high}(t = D180) - \widehat{CDF}_{trt,high}(t = D180)]$$

Its 95% CI is the above estimate of difference

$$\pm 1.96 * \sqrt{w^2 * (SE(\widehat{CDF}_{pbo,standard}(t = D180)))^2 + (SE(\widehat{CDF}_{trt,standard}(t = D180)))^2 + (1 - w)^2 * (SE(\widehat{CDF}_{pbo,high}(t = D180)))^2 + SE(\widehat{CDF}_{trt,high}(t = D180))^2)}$$

with weight w defined by inverse of variance in two baseline GVHD risk groups. That is:

$$w = \frac{1/[SE(\widehat{CDF}_{pbo,standard}(t=D180))^2 + SE(\widehat{CDF}_{trt,standard}(t=D180))^2]}{1/[SE(\widehat{CDF}_{pbo,standard}(t=D180))^2 + SE(\widehat{CDF}_{trt,standard}(t=D180))^2] + 1/[SE(\widehat{CDF}_{pbo,high}(t=D180))^2 + SE(\widehat{CDF}_{trt,high}(t=D180))^2]}$$

In order to conduct above hypothesis testing for NRM at Day 180, time to NRM, defined as the interval between randomization and death due to causes other than malignancy relapse, will be derived. All subjects in the FAS without a death due to causes other than malignancy relapse will be censored at either study withdrawal, death due to malignancy relapse, or the date of last contact before or on the cutoff date, whichever is earliest.

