7.4.2. Survival Analyses of Nonrelapse Mortality

Time to death due to causes other than malignancy relapse (NRM) will be analyzed according to the randomized treatment group and strata assigned at randomization.

The hazard ratio of itacitinib relative to placebo overall [REDACTED] will be calculated, along with its 95% CI, using a stratified Cox model.

Stratified log-rank test will also be used to test survival curve of NRM in the treatment group relative to placebo group using the FAS.

Subgroup KM analyses of NRM will also be conducted by Day 28 response status [REDACTED].

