7.4.3. Competing-Risks Analyses of Nonrelapse Mortality

In the literature, analyzing NRM is normally conducted in the context of a competing-risks situation. Time from randomization to first occurrence of NRM or competing event is observed and used for analysis; otherwise, the subject is censored. Nonrelapse mortality and a competing-risk event are mutually exclusive. This is because a subject either dies due to malignancy relapse, dies due to an event other than malignancy relapse, or is censored at last follow-up. There are 2 types of competing-risks analyses:

- I: Time to NRM competing with time to malignancy relapse
Time to first occurrence of either death due to reasons other than malignancy relapse (NRM) or malignancy relapse is defined as an event of interest and competing risk event, respectively. Subjects without an event (neither event of interest nor competing event) will be censored at the date of study withdrawal or date of last contact before or on the cutoff date, whichever is the earlier.
- II: Time to NRM competing with time to death due to malignancy relapse
Time to first occurrence of either death due to reasons other than malignancy relapse (NRM) or death due to malignancy relapse is defined as an event of interest and competing risk event, respectively. Subjects without an event (neither event of interest nor competing event) will be censored at the date of study withdrawal or date of last contact before or on the cutoff date, whichever is the earlier.

For each of the competing-risks analyses (ie, I and II), there are 2 ways of modeling conducted in this study. The first one is cause-specific hazard modeling and the second one is subdistribution hazard modeling.

In cause-specific hazard modeling, competing events will be censored, and a stratified log-rank test [REDACTED] will be used to test 2 KM curves with KMC estimate equals 1 minus KM estimate. In cause-specific hazard modeling, stratified Cox regression model [REDACTED] with a cofactor of treatment group will be used to estimate cause-specific hazard ratio (itacitinib vs placebo) and 95% CI.

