In subdistribution hazard modeling, competing-risk events will be considered to remain in the risk set as described by Gray (1988). Stratified Gray's test [REDACTED] will be used to test equality of 2 cumulative incidence curves. Cumulative incidence function at Day 180 (SE) will be estimated. Stratified subdistribution hazard regression (Fine and Gray 1999) with cofactor of treatment group (itacitinib vs placebo) will be performed, and subdistribution hazard ratio (95% CI) on treatment effect (itacitinib vs placebo) will be estimated.

Cumulative incidence curve for each competing-risk analysis will be plotted overall by Day 28 response status [REDACTED]

7.4.4. Overall Response Rate at Days 14, 56, 100, and 180

Similar to Day 28 ORR, ORR at Days 14, 56, 100, and 180, respectively, is defined as the proportion of subjects demonstrating a CR, VGPR, or PR at a defined analysis visit/window (ie, ± 3 days of scheduled visit date).

The ORR on Days 14, 56, 100, and 180 will be estimated with a 95% CI. The proportion of responders will be estimated with 95% CIs. Confidence intervals will be calculated based on the exact method for binomial distributions. Summary statistics will be provided.

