7.4.9. Failure-Free Survival

Failure-free survival is defined as the proportion of subjects who are still alive, have not relapsed of underlying hematologic disease, have not required additional therapy for aGVHD, and have not had signs or symptoms of cGVHD. Subjects without an event of relapse of underlying hematologic disease, death due to relapse, death due to causes other than relapse, initiation of new anti-GVHD therapy, or signs or symptoms of cGVHD will be censored at the date of study withdrawal or the date of last contact before or on the data cutoff date, whichever is earlier. After randomization, the FFS event date will be the first occurrence of one of the following:

- Initiation of anti-GVHD therapy, or
- Relapse/recurrence of underlying hematologic disease, or
- Death due to malignancy relapse, or
- Death due to causes other than malignancy relapse, or
- Signs or symptoms of cGVHD.

Failure free survival will be analyzed according to the randomized treatment group and strata assigned at randomization.

The survival distribution of FFS in each treatment group overall [REDACTED] will be estimated using the KM method, and the KM curves; medians; 1-, 2-, 6-, 12-, 18-, and 24-month (at Days 30, 60, 180, 365, 547, and 730, respectively) survival estimates, and 95% CIs will be presented (Brookmeyer and Crowley 1982). The hazard ratio of treatment relative to placebo overall [REDACTED] will be calculated, along with its 95% CI, using a stratified Cox model. Stratified log-rank test will also be used to test FFS survival curve in the itacitinib group against the placebo group.

Subgroup KM analyses of FFS will also be conducted by Day 28 response status [REDACTED]

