7.4.10. Overall Survival

Overall survival is defined as the time from randomization to death due to any cause during the study. The KM method will be used to estimate the survival time distribution and the median survival. Subjects with no observed death or loss to follow-up will be treated as censored at either the date of study withdrawal or the date of last contact prior to or on the data cutoff date, whichever is later.

Overall survival will be analyzed according to the randomized treatment group and strata assigned at randomization.

The survival distribution of OS in each treatment group overall [REDACTED] will be estimated using the KM method, and the KM curves; medians; 1-, 2-, 6-, 12-, 18-, and 24-month (at Days 30, 60, 180, 365, 547, and 730, respectively) survival estimates, and 95% CIs will be presented (Brookmeyer and Crowley 1982). The hazard ratio of itacitinib relative to placebo overall [REDACTED] will be calculated, along with its 95% CI, using a stratified Cox model. Stratified log-rank test will also be used to test the OS survival curve in the itacitinib group against the placebo group.

Subgroup KM analyses of OS will also be conducted by Day 28 response status [REDACTED].

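### NRM, OS and (by implication) FFS curves split by Day 28 response start at randomisation with no legible landmark, so responders gain a built-in advantage

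*SAP*

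**What the plan says.** Four SAP sections split a time-to-event outcome by Day 28 response:

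- 7.4.2 (NRM): "Subgroup KM analyses of NRM will also be conducted by Day 28 response status"
- 7.4.3 (NRM, competing risks): "Cumulative incidence curve for each competing-risk analysis will be plotted overall by Day 28 response status"
- 7.4.9 (FFS): "Subgroup KM analyses of FFS will also be conducted by Day 28 response status"
- 7.4.10 (OS): "Subgroup KM analyses of OS will also be conducted by Day 28 response status"

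The clock starts at randomisation for NRM and OS. SAP 7.4.1.2 has time to NRM "defined as the interval between randomization and death due to causes other than malignancy relapse". SAP 7.4.3 states: "Time from randomization to first occurrence of NRM or competing event is observed and used for analysis". SAP 7.4.10 states: "Overall survival is defined as the time from randomization to death due to any cause during the study". FFS has no separate sentence on its origin, but 7.4.9 implies the same one: "After randomization, the FFS event date will be the first occurrence of one of the following".

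SAP 7.3.1.1 accepts a response assessed within 3 days of Day 28. It counts death, study withdrawal or new anti-GVHD therapy before the Day 28 visit as nonresponse.

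No legible text starts these curves at Day 28 or limits them to subjects alive then. The only legible Day 28 clock is in SAP 7.3.3, for the two alternative duration-of-response definitions in Day 28 responders. Text is redacted directly after each of the four sentences.

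**The concern.** Grouping by an event that can only be observed around Day 28, while counting time from randomisation, produces immortal-time bias. No responder can die before the response assessment, and every subject who does die before it is a nonresponder by definition. The direction of the bias follows from the SAP's own definitions. FFS is affected twice, because early new anti-GVHD therapy is both a nonresponse (7.3.1.1) and an FFS event (7.4.9).

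Protocol 1.4.3 justifies the primary endpoint by its prognostic value for 6-month and 2-year NRM. Readers are likely to use these curves to judge that link in this trial. The artefact would add to any true association and could suggest one where none exists.

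**Working it through.** The documents state no outcome by Day 28 response, so there is no planned figure to reproduce. The calculation below sizes the artefact alone.

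**Inputs from SAP 3.3.** Day 28 ORR is 56% on placebo and 72% on itacitinib. Day 180 NRM is 33% and 19.8%.

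**Assumptions.** NRM has a constant hazard to Day 180, response is assessed on Day 28, subjects are followed to Day 180, and among Day 28 survivors response is unrelated to later death.

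**Formulas.** Let *h* = −ln(1 − NRM)/180, *d* = 1 − exp(−28*h*) (death before assessment) and *F* = NRM at the time point read.

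- Responders: R = (F − d)/(1 − d)
- Nonresponders: N = (F − ORR × R)/(1 − ORR)
- Gap: N − R = d(1 − F)/[(1 − d)(1 − ORR)]. This is above zero whenever d > 0 and F < 1.

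**Day 180**

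| | Placebo | Itacitinib |
|---|---|---|
| h per day | −ln(0.67)/180 = 0.002225 | −ln(0.802)/180 = 0.001226 |
| d | 0.0604 | 0.0337 |
| R | (0.33 − 0.0604)/0.9396 = 28.7% | (0.198 − 0.0337)/0.9663 = 17.0% |
| N | (0.33 − 0.56 × 0.287)/0.44 = 38.5% | (0.198 − 0.72 × 0.170)/0.28 = 27.0% |
| Gap | 9.8 points | 10.0 points |

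**Day 30.** This applies only if the listed 1-month estimate is also read off these curves. Placebo F = 0.0646 gives 0.4% against 14.1%, a gap of about 14 points. Itacitinib F = 0.0361 gives 0.2% against 12.3%, about 12 points.

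**Sensitivity to early death**

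- Placebo with d = 0.02: gap 3.1 points. With d = 0.10: gap 16.9 points.
- Weibull shape from 0.7 to 2 in place of a constant hazard: gap from about 17.5 down to 1.5 points.
- Assessment on Day 25 or Day 31 (placebo): 8.7 or 10.9 points.

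**How visible the artefact would be.** In 5,000 simulated trials with no true link, a two-sided 5% log-rank comparison of responders with nonresponders was significant in 44% of runs (218 subjects, placebo rates), 47% (218, itacitinib rates) and 75% (436 pooled, using the midpoints ORR 64% and NRM 26.4%). With a Day 28 landmark the rates were 4.8%, 5.3% and 4.3%. The legible SAP plans no such test; this only shows how strong the artefact is.

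**What a landmark leaves**

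- Visits spread uniformly over Days 25 to 31 (simulation): the gap is 9.7 and 10.0 points from randomisation, 0.3 in each arm with a Day 28 landmark, and 0.0 with a Day 31 landmark.
- Extreme case for a Day 28 landmark, every visit on Day 31 (placebo): d = 1 − exp(−3h) = 0.0067, F = 1 − exp(−152h) = 0.287, and ORR among survivors is 0.56/0.9396 = 0.596. The gap is 1.2 points.
- If 10% of visits slip to Days 32 to 38 (an assumption; Protocol 6.2 allows delay for safety): 0.6 point with Day 28, and 0.1 (placebo) and 0.2 (itacitinib) with Day 31.

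No figure is given for OS or FFS, because the documents give no planning rates for them.

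**The case against.** The strongest objection is the redaction. Text is hidden after all four sentences, and part of the display list in SAP Appendix B cannot be read, so a landmark rule may exist out of sight. This stands as a limit on confidence. SAP 10.2.1 lists redacted items beside Day 28 response status as added subgroup factors, which points to further subgroups rather than a landmark but does not prove it.

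Second, these sentences sit in sections that compare the arms, so the plan may mean itacitinib against placebo within each response group. The gap described here would not then arise. That comparison would still condition on a post-randomisation outcome and would need a descriptive label. The wording in 7.4.3 supports a responder-versus-nonresponder display, though not conclusively.

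Third, Day 28 response status is not defined as a two-way split. SAP 7.3.2 also uses the term, for duration of response, where it could mean CR, VGPR or PR. A finer split would change the figures, but early deaths would still sit with the nonresponders unless shown as a separate group.

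Fourth, the size rests on assumed death timing, the listed time points are attached to treatment-group estimates rather than to these subgroups, and the displays are supportive. All of this is true. It limits the priority of the point but does not remove the mechanism.

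**Conclusion.** The concern holds on the legible text. Followed as written, a responder-versus-nonresponder display of NRM or OS, and by implication FFS, has a gap that comes from the definitions alone. On the planning rates it is about 10 points of Day 180 NRM in either arm. That figure assumes a constant hazard and no true link; the plausible size depends on early mortality, which the documents do not give. The primary ORR test, the key secondary NRM test, the randomised comparisons and type I error control are unaffected. This should be corrected, with medium confidence because of the redactions.

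**What to change.** Make each analysis by Day 28 response a landmark analysis in 7.4.2, 7.4.3, 7.4.9 and 7.4.10:

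- Include only subjects alive, in follow-up and free of that endpoint's event at the landmark.
- Keep the 7.3.1.1 response class, and count the clock and any listed time points from the landmark.
- Use study Day 28, counted from randomisation for subjects never dosed, because SAP 4.1.1 sets Day 1 at first dose. This matches the 7.3.3 clock. Day 31, the end of the visit window, is an option that removes the remainder for in-window visits.
- Label any comparison of arms within response groups as descriptive. A landmark does not remove post-randomisation selection.

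The cost is one sentence per section and a minor programming change. Events before the landmark leave these displays only: at constant hazard, about 13 NRM deaths on placebo (218 × 0.0604) and 7 on itacitinib (218 × 0.0337). They stay in the randomised analyses. For FFS, a Day 31 landmark would also drop new therapy started after the Day 28 visit, which can flatter the nonresponder curve, so Day 28 is preferable there. Time points in these displays would no longer be counted from randomisation. If the redacted text already sets such a rule, no change is needed.

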7.5. Other Secondary Efficacy Analyses

Secondary graft failure will be tabulated with summary statistics.

Incidence rate of aGVHD flares through Day 100 will be summarized. Summary statistics will be provided.

Average and cumulative corticosteroid dose during the weeks ending on Days 28, 56, 100, and 180 will be tabulated. Proportions of subjects who discontinue corticosteroids will be summarized.

Proportions of subjects who discontinue immunosuppressive medication on Days 56 and 100 will be tabulated. Summary statistics will be provided.

Incidence of cGVHD (Days 180 and 365 and overall) will be estimated. Summary statistics will be provided.

[REDACTED]

Subgroup analyses will be conducted by underlying hematologic disease (malignant vs nonmalignant), as appropriate.

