Evaluate the use and discontinuation of corticosteroids.	Average and cumulative corticosteroid dose at Days 28, 56, 100, and 180; proportion of subjects who discontinue corticosteroids at Days 56 and 100.
Evaluate the use and discontinuation of immunosuppressive medications.	Proportion of subjects who discontinue immunosuppressive medications at Days 56 and 100.
Evaluate the incidence of aGVHD flares.	Incidence rate of aGVHD flares through Day 100.
Evaluate the incidence of cGVHD.	Incidence rate of cGVHD at Days 180 and 365.

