6.5. Exposure

For subjects in the safety analysis set, exposure to study drug will be summarized descriptively as follows:

- **Duration of treatment with study drug:**

Duration of treatment (days) = Date of last dose of study drug – Date of first dose of study drug + 1

- **Average daily dose of study drug:**

Average daily dose of study drug (mg/day) = [total actual study drug dose taken (mg)] / [duration of treatment with study drug]

Frequency distribution of itacitinib/placebo duration category (days) will be tabulated by concatenated intervals: Day 1 through Day 28, Day 29 through Day 100, Day 101 through Day 180, and > Day 180.

Similarly, duration of corticosteroid and average daily dose of corticosteroid before EOT as the background therapy will be summarized by treatment group. Frequency distribution of corticosteroid duration category (days) will be tabulated by concatenated intervals.

Frequency distribution of itacitinib/placebo dose modification in the treatment phase (ie, dose decreased due to toxicity, dose increased, dose tapered, dose temporarily interrupted and with previous dose resumed) will be tabulated by concatenated intervals: Day 1 through Day 28, Day 29 through Day 56, Day 57 through Day 84, Day 85 through Day 112, Day 112 through Day 140, Day 141 through Day 168, Day 169 through Day 196, Day 197 through Day 224, Day 225 through Day 252, Day 253 through Day 280, Day 281 through Day 308, Day 381 through Day 336, Day 337 through Day 365, and > Day 365.

In order to summarize corticosteroid use over time in the treatment phase, for days of interest Day X (ie, X = 14, 28, 56, 100, and 180, separately), average corticosteroid dose (mg/day) during the week ending on Day X, relative corticosteroid dose (%) during the week ending on Day X will be summarized by treatment group. Number and percentage of subjects ongoing with itacitinib/placebo and ongoing with corticosteroid on Day X respectively will be summarized by treatment group.

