10.1. Changes to Protocol-Defined Analyses

Note that the FAS population is equivalent to the efficacy evaluable population as defined in the protocol.

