2.2.31	Cox Regression Analysis of Overall Survival	FAS		X
████	██	████		█
████	██	████		█
2.2.34	Summary of Post-Transplant Lymphoproliferative Disorder Assessment	FAS		X
2.2.35	Summary of ECOG Status in the Treatment Phase	FAS		X
2.2.36	Summary of Death	FAS		X
2.2.37	Summary of Relapse of Underlying Hematologic Disease	FAS		X
Exposure				
3.1.1	Summary of Itacitinib Dose Modifications in the Treatment Phase	Safety		X
3.1.2	Summary of Corticosteroid Exposure Prior to Day 1	Safety		X
3.1.3	Summary of Corticosteroid Exposure in the Treatment Phase	Safety		X
3.1.4	Summary of Corticosteroid Exposure Between Day 1 and Start of New Anti-GVHD Therapy	Safety		X
3.1.5	Summary of Corticosteroid Use Over Time in the Treatment Phase	Safety		X
3.1.4.1	Summary of Itacitinib/Placebo Exposure and Compliance in the Treatment Phase	Safety		X
3.1.4.2	Summary of Itacitinib/Placebo Exposure and Compliance in the Treatment Phase by Age Group	Safety		X
3.1.4.3	Summary of Itacitinib/Placebo Exposure and Compliance in the Treatment Phase by Sex	Safety		X
3.1.4.4	Summary of Itacitinib/Placebo Exposure and Compliance in the Treatment Phase by Race	Safety		X
3.1.4.5	Summary of Itacitinib/Placebo Exposure and Compliance in the Treatment Phase by Region	Safety		X
Adverse Events				
3.2.1.1	Overall Summary of Treatment-Emergent Adverse Events in the Treatment Phase	Safety	X	X
3.2.1.2	Overall Summary of Treatment-Emergent Adverse Events in the Treatment Phase by Age Group	Safety	X	X
3.2.1.3	Overall Summary of Treatment-Emergent Adverse Events in the Treatment Phase by Sex	Safety	X	X
3.2.1.4	Overall Summary of Treatment-Emergent Adverse Events in the Treatment Phase by Race	Safety	X	X
3.2.1.5	Overall Summary of Treatment-Emergent Adverse Events in the Treatment Phase by Region	Safety	X	X
3.2.2	Summary of Treatment-Emergent Adverse Events in the Treatment Phase by MedDRA System Organ Class and Preferred Term	Safety	X	X
3.2.3	Summary of Treatment-Emergent Adverse Events in the Treatment Phase by MedDRA Preferred Term in Decreasing Order of Frequency	Safety	X	X
3.2.4	Summary of Treatment-Emergent Adverse Events in the Treatment Phase by MedDRA System Organ Class, Preferred Term, and Highest Grade	Safety	X	X
3.2.5.1	Summary of Grade 3 or Higher Treatment-Emergent Adverse Events in the Treatment Phase by MedDRA System Organ Class and Preferred Term	Safety	X	X

Table No.	Title	Population	Standard	In-Text

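### SAP 7.5 limits the cumulative corticosteroid dose to the week ending on Days 28, 56, 100 and 180, which is not the cumulative dose at those days that the protocol and SAP Table 1 name

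*SAP*

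**What the plan says.** The endpoint appears in the protocol synopsis, in the objectives table of protocol section 2 and in protocol 9.4.2. SAP Table 1 (section 2.2) repeats it: "Average and cumulative corticosteroid dose at Days 28, 56, 100, and 180". None of these places attaches a weekly window. The objective it serves concerns how corticosteroids are used and stopped.

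SAP 7.5 is the only visible SAP text that says how this endpoint will be analysed. It reads: "Average and cumulative corticosteroid dose during the weeks ending on Days 28, 56, 100, and 180 will be tabulated".

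SAP 6.5 plans two further steroid summaries by treatment group. At Days 14, 28, 56, 100 and 180 it gives "average corticosteroid dose (mg/day) during the week ending on Day X, relative corticosteroid dose (%) during the week ending on Day X". Over the whole treatment period it says that "duration of corticosteroid and average daily dose of corticosteroid before EOT as the background therapy will be summarized by treatment group". In the visible list of planned displays, Tables 3.1.2 to 3.1.5 deal with steroid exposure; the last is titled "Summary of Corticosteroid Use Over Time in the Treatment Phase". No visible title names a cumulative dose to a landmark day.

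SAP 10.1, on changes to protocol-defined analyses, contains one sentence: "Note that the FAS population is equivalent to the efficacy evaluable population as defined in the protocol". SAP 10.2.1 does not mention a steroid window.

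**The concern.** A cumulative dose at Day X would ordinarily mean everything given up to Day X. SAP 7.5 places both the average and the cumulative dose inside a single week. Dose given before that week is dropped, and two separately named quantities become one.

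This matters because the documents leave steroid tapering to institutional guidelines, at a pace that follows resolution of GVHD (protocol synopsis and 5.2.3). The timing of dose reduction can therefore differ between subjects and between arms. Total dose to a landmark reflects that timing. A last-week dose records only where the taper has got to. By Days 100 and 180, any subject already off steroids for a week scores zero, whatever was given earlier. A descriptive comparison of steroid exposure built on the table as written would not be the one the protocol names.

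**Working it through.** The plan gives no figure to reproduce. The check compares the two definitions, then uses an illustration.

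**Definitions.** Let d(t) be the steroid dose on study day t.

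- Endpoint as named, with accumulation assumed to start on Day 1: C(X) = sum of d(t) for t = 1 to X.
- SAP 7.5 as written: W(X) = sum of d(t) for t = X−6 to X.
- Weekly average over all seven days: A(X) = W(X) / 7, so W(X) = 7 × A(X).

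The weekly sum is a fixed multiple of the weekly average.

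**Share of days covered** (7 / X):

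| Day X | Week | Share of Days 1 to X |
|---|---|---|
| 28 | 22–28 | 7/28 = 25.0% |
| 56 | 50–56 | 7/56 = 12.5% |
| 100 | 94–100 | 7/100 = 7.0% |
| 180 | 174–180 | 7/180 = 3.9% |

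**Illustration.** These two courses are assumed for arithmetic only and are not from the documents. Both start at 2 mg/kg per day and reach zero at Day 56. Course A falls linearly from Day 7; course B is held to Day 28 and then falls linearly.

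- C(56) for A: 7 × 2 + 2 × (49 − 25) = 14 + 48 = 62 mg/kg.
- C(56) for B: 28 × 2 + 2 × (28 − 14.5) = 56 + 27 = 83 mg/kg.

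| Day X | W(X), A | W(X), B | C(X), A | C(X), B |
|---|---|---|---|---|
| 28 | 8.86 | 14.00 | 46.57 | 56.00 |
| 56 | 0.86 | 1.50 | 62 | 83 |
| 100 | 0 | 0 | 62 | 83 |
| 180 | 0 | 0 | 62 | 83 |

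Total exposure differs by 83 − 62 = 21 mg/kg from Day 56 onward. The weekly sums differ by 1.50 − 0.86 = 0.64 mg/kg at Day 56 and by nothing at Days 100 and 180. At Day 28 the weekly sums do separate the courses (8.86 against 14.00).

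**Whether SAP 6.5 supplies the total.** By analogy with its study-drug formula, average daily dose is total dose divided by duration, so a subject's total to end of treatment is duration × average. That total stops at end of treatment, which varies by subject and may vary by arm. It is not C(28), C(56), C(100) or C(180). A group total also cannot be rebuilt from separate summaries of duration and average, because the mean of a product is not in general the product of the means.

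**The case against.** The best defence is that the wording is loose and the endpoint has not been changed. SAP Table 1 keeps the protocol's endpoint, SAP 10.1 declares no change, and a one-week cumulative dose is so redundant that the window may have been meant for the average alone, as in SAP 6.5 ("average corticosteroid dose (mg/day) during the week ending on Day X"). The plural in SAP 7.5 could even be stretched to mean all weeks up to each day. This may be what was intended. It is not what the sentence says: the window governs both quantities, and the plural is naturally explained by four named days with one week each. If the intent was different, the sentence still needs correcting.

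Three stronger conclusions are tempting, and the documents do not support them.

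- *That total steroid dose will never be produced.* The visible display list starts partway through, some rows are redacted, and SAP 7.5 contains a redacted block. Tables 3.1.3 and 3.1.4 cover steroid exposure in the treatment phase and from Day 1 until new anti-GVHD therapy, and may include a total. What can be said is that the visible text specifies no total to any of the four days.
- *That a difference in early exposure would be invisible.* SAP 6.5 also reports the week ending on Day 14. Take two assumed courses to Day 28: 2 mg/kg for 21 days then 0.5 for 7 (42 + 3.5 = 45.5 mg/kg), and 2 mg/kg for 7 days then 0.5 for 21 (14 + 10.5 = 24.5 mg/kg). Both give 3.5 mg/kg in the last week, but the Day 14 average is 2 against 0.5 mg/kg per day. The weekly averages and the end-of-treatment summaries show exposure in part.
- *That a formal steroid-sparing objective is lost.* The stated objective is to describe use and discontinuation. Protocol 9.4.2 specifies no between-arm test for this item, and SAP 3.2 applies no multiplicity adjustment beyond the primary and key secondary endpoints.

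**Conclusion.** The point holds in a limited form. SAP 7.5 as written yields the wrong quantity for a named secondary endpoint: a rescaled weekly average covering between 25.0% (Day 28) and 3.9% (Day 180) of the days the endpoint implies. SAP 10.1 and 10.2.1 do not declare the departure. The consequence is confined to a descriptive secondary endpoint; the Day 28 response and Month 6 nonrelapse mortality tests are untouched.

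The conclusion rests on two assumptions. One is that accumulation starts on Day 1, the natural reading, which the protocol does not state. The other is that the weekly average is taken over all seven days. The gap concerns the visible SAP text only, and the illustrative courses show the mechanism without predicting the size of any difference in this trial.

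**What to change.** In SAP 7.5, define cumulative corticosteroid dose at Day X (28, 56, 100, 180) as the sum of daily steroid-equivalent dose from Day 1 through Day X. State the equivalence used to combine prednisone and methylprednisolone, and the unit; SAP 6.5 already works in mg/day, so mg would be consistent, and mg/kg is a matter of choice. Add rules for subjects who die before Day X, for doses after end of treatment, and for missing dose records. Keep the weekly average as a separate display and name the table that will carry the cumulative dose. If a one-week quantity is really intended, drop the word cumulative and declare and justify the change in SAP 10.1.

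The cost is a few sentences and one derived variable. The main difficulty is data after end of treatment: the schedules of assessments mark steroid dose monitoring through end of treatment and re-treatment, but not in follow-up. Listing 2.5.3, on steroid use after end of treatment, suggests some capture, but its completeness is not stated. The number of subjects with complete dose records to each day should be shown beside the result.
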